4.2.2.2 Restrictions on diet and life style

No specific restrictions on diet or life style of the patients are required.

4.2.2.3 Restrictions regarding women of childbearing potential

Women of child bearing potential must maintain an adequate contraception throughout the course of the trial as described in patient information and up to 20 weeks after the last study drug infusion.

4.3 TREATMENT COMPLIANCE

Compliance will be assured by administration of all trial medication in the study center under the supervision of the investigating physician or a designee. The measured plasma concentrations will provide additional confirmation of compliance.

Patients who are non-compliant (for instance, who do not appear for scheduled visits) may be removed from the trial and the CRFs completed accordingly (for further procedures, please see [Section 3.3.4.1](#)).

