3.3.4 Withdrawal of patients from therapy or assessments

Patients may potentially be withdrawn from trial treatment or from the trial as a whole ("withdrawal of consent") with very different implications, please see [Sections 3.3.4.1](#) and [3.3.4.2](#) below.

Every effort should be made to keep the randomised patients in the trial: if possible on treatment, or at least to collect important trial data.

Measures to control the withdrawal rate include careful patient selection, appropriate explanation of the trial requirements and procedures prior to randomization, as well as the explanation of the consequences of withdrawal.

The decision to withdraw from trial treatment or from the whole trial as well as the reason must be documented in the patient files and Case Report Form (CRF).

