3.3.4.1 Withdrawal from trial treatment

An individual patient is to be withdrawn from trial treatment if:

- The patient wants to withdraw from trial treatment, without the need to justify the decision.
- The patient needs to take concomitant drugs that interfere with the investigational product or other trial medication. Please refer to [Section 4.2.2](#) for restricted medication during this trial.
- The patient can no longer be treated with trial medication for other medical reasons (such as surgery, adverse events, other diseases, or pregnancy).
- The patient has repeatedly shown to be non-compliant with important trial procedures and, in the opinion of both, the investigator and sponsor representative, is not willing or able to stick to the trial requirements in the future.

Given the patient's agreement, the patient will undergo the procedures for the remaining scheduled visits and follow up as outlined in the [Flow Chart](#).

Should the patient not agree to continue the remaining trial visits as scheduled after the premature treatment discontinuation, all efforts should be made to bring the patient to the primary endpoint visit at Week 16 (Day 113, V11), and/or at least to the End of Trial at Week 32 (Day 225, V13).

For all patients the reason for withdrawal from trial treatment (e.g. adverse events) must be recorded in the CRF. These data will be included in the trial database and reported.

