7.5 HANDLING OF MISSING DATA

Every effort will be made to collect complete data at all visits. However, missing data will still occur and approaches to handle this are proposed below.

With respect to safety evaluations, it is not planned to impute missing values.

For all binary endpoints (i.e. endpoints that are either 1 (patient responded) or 0 (patient did not respond)), the following will be performed:

- If there are data at visits both before and after the visit with a missing outcome, then impute as success only if both neighbouring visits also represent a success;
- Otherwise, impute as a failure to achieve a response (i.e. NRI [No Response Imputation]).

If a patient takes a rescue medication for the treatment of palmoplantar pustulosis prior to observing the primary endpoint for this trial, then all data subsequent to the intake of such rescue will be considered to represent a failure to achieve a response. Further details on what constitutes a rescue intake with potential impact on efficacy outcomes will be described in the TSAP.

For secondary efficacy endpoints which are continuous in nature, the use of a restricted maximum likelihood (REML)-based mixed model repeated measures (MMRM) approach will ensure that missing data are handled implicitly, via a missing at random assumption, by the statistical model.

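### Section 4.3 lets sites remove non-compliant patients from the trial, while the section it cites provides only for withdrawal from treatment with continued follow-up

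*Protocol*

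**What the plan says.** Section 4.3 (Treatment compliance) begins its rule with "Patients who are non-compliant (for instance, who do not appear for scheduled visits" and says that such patients "may be removed from the trial and the CRFs completed accordingly". It then refers to section 3.3.4.1 for further procedures.

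Section 3.3.4 separates withdrawal from treatment from withdrawal from the trial as a whole. It labels the second as withdrawal of consent and warns that the implications differ greatly. Its general principle is "Every effort should be made to keep the randomised patients in the trial".

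Section 3.3.4.1 opens with "An individual patient is to be withdrawn from trial treatment if". One of its listed reasons is "The patient has repeatedly shown to be non-compliant with important trial procedures", and both the investigator and the sponsor representative must hold that opinion. If the patient agrees, "the patient will undergo the procedures for the remaining scheduled visits and follow up". If not, all efforts go into reaching the Week 16 visit and/or at least the Week 32 visit.

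Section 6.1 says that a missed appointment is rescheduled if possible. Section 6.2.3 keeps patients who stop treatment early on the visit schedule to Week 32.

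Section 7.5 imputes a missing binary outcome as success only when the visits on both sides are successes. The default is "Otherwise, impute as a failure to achieve a response".

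**The concern.** Section 4.3 describes an exit that fits neither of the two in section 3.3.4: the site takes a patient out of the trial although the patient has not withdrawn consent. The section it cites has no procedure for that. A site has to choose between the literal words of 4.3 and the follow-up rules elsewhere.

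Both primary endpoints are at stake. If a reachable patient is removed before Week 16, the ppPASI50 status is replaced by non-response whatever the patient's true state. The other primary endpoint is the number of patients with drug-related adverse events. Under section 5.3.6.2, active adverse event collection runs only to the individual patient's end of trial, so removal shortens the period in which such events are sought.

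**Working it through.** **1. The texts side by side**

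| Point | Section 4.3 | Sections 3.3.4 and 3.3.4.1 |
|---|---|---|
| Trigger | Non-compliance; non-attendance is the example | Repeated non-compliance with important procedures, and unwilling or unable to comply in future |
| Who decides | Not stated | Investigator and sponsor representative, both |
| What the patient leaves | The trial | Trial treatment; leaving the trial is tied to withdrawal of consent |
| Data afterwards | CRFs are completed; nothing further stated | Remaining visits if the patient agrees; otherwise Week 16 and/or at least Week 32 |

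The rows differ on every point. Sections 6.1 and 6.2.3 agree with the right-hand column.

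**2. What a removal does to the endpoints**

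- Removal before the Week 16 assessment: no later visit exists, so the neighbouring-visit condition in 7.5 cannot be met and Week 16 is a failure.
- Week 16 missed but the patient seen later: the condition can be met, and success is possible. Literal removal closes this route.
- Removal after Week 16: ppPASI50 stands as observed, and only follow-up data are lost.
- Safety: the residual effect period is 20 weeks after the last dose (7.3.4). With the last dose at Week 12, it ends at Week 12 + 20 = Week 32. Removal stops scheduled visits and active collection inside that period. Relevant SAEs and AESIs that the investigator learns of are still reported, and persisting adverse events are still followed (5.3.6.2).

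**3. Size for one patient**

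There are 20 patients per arm (7.7), so one responder scored as a failure moves the arm by 1/20 = 5 percentage points. The decision thresholds are 0.20 × 20 = 4 patients (Scenario 1) and 0.15 × 20 = 3 patients (Scenario 2).

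**4. Reproducing Table 7.7:1**

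Inputs from 7.7: three independent Binomial(20, p) arms, true difference 0.30 for both doses, placebo rate 0.15 to 0.30. With X the number of responders:

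- Scenario 1 = P[max(X300, X900) − Xplacebo ≥ 4]
- Scenario 2 = P[Scenario 1 met and X300 − Xplacebo ≥ 3]

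Exact enumeration agrees with the table once the results are cut to whole percentages.

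| Placebo rate | Scenario 1: table | Scenario 1: exact | Scenario 2: table | Scenario 2: exact |
|---|---|---|---|---|
| 0.15 | 93% | 93.6% | 87% | 87.6% |
| 0.20 | 92% | 92.7% | 86% | 86.4% |
| 0.25 | 91% | 91.9% | 85% | 85.6% |
| 0.30 | 91% | 91.4% | 85% | 85.1% |

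**5. Illustration with removals**

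Let a share d of every arm be removed before Week 16 and scored as failures, unrelated to true response. Each rate p becomes p(1 − d), and the expected difference becomes 0.30(1 − d). That is 0.285 at d = 5% and 0.27 at d = 10%. The protocol gives no d; both values are assumptions.

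| Placebo rate | Scenario 1, d = 5% | Scenario 2, d = 5% | Scenario 1, d = 10% | Scenario 2, d = 10% |
|---|---|---|---|---|
| 0.15 | 92.2% | 85.4% | 90.5% | 82.9% |
| 0.20 | 91.1% | 84.1% | 89.3% | 81.6% |
| 0.25 | 90.3% | 83.2% | 88.5% | 80.6% |
| 0.30 | 89.7% | 82.6% | 87.8% | 79.9% |

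**The case against.** The best defence is that 4.3 uses a permissive verb and cites 3.3.4.1, whose rules keep the patient in follow-up. Read with 6.1 and 6.2.3, the intention is clear enough, and 4.3 is loosely worded. Much of this stands: a reader might infer a deliberate third route out of the trial, and the cross-reference speaks against that. It does not settle the conflict, because 3.3.4.1 contains nothing about removal from the trial and a site can still act on the literal words.

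Several stronger readings also fail:

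- A reader might infer that every removal becomes a Week 16 failure. That holds only for removal before the Week 16 assessment with no later visit.
- A reader might infer that safety follow-up is lost altogether. Section 5.3.6.2 still covers relevant SAEs and AESIs that become known, and persisting events. Drug-related events already recorded still count.
- A reader might read the reduced probabilities as a shortfall in the design. Many patients who do not attend would have no Week 16 value whatever 4.3 said, and the calculation charges all of that loss to this one sentence. The increment due to 4.3 could be near zero. Section 7.7 also sets a minimum probability of 0.80. At 5% removal every figure exceeds it; at 10% only one does not (79.9%).
- A reader might infer loss that differs by arm. If 10% were removed from placebo only and there were no true effect, the same enumeration puts the Scenario 1 false positive rate at 13.1-25.4%, against the stated 20% control. Nothing in the protocol points to such a pattern, and the double blind limits removal decisions that depend on arm.

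**Conclusion.** The contradiction is in the current text and should be resolved. Section 4.3 permits something that 3.3.4 and 3.3.4.1 do not provide for, with a looser trigger and no named decision-maker. A literal reading would give up Week 16 and adverse event data that could still be obtained from a consenting patient.

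The certain part of the size is 5 percentage points of an arm for each responder removed before Week 16. The effect on the trial's success probability is unknown. The figures for 10% removal (87.8-90.5% and 79.9-82.9%) show the most that 4.3 could cost at that assumed rate, because all the loss is attributed to it. They rest on equal removal in all arms and on removal being unrelated to response. Table 7.7:1 is not in error.

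**What to change.** Reconcile 4.3 with 3.3.4, 3.3.4.1, 6.1 and 6.2.3. Section 4.3 should state that, whatever is decided about trial medication, collection of outcome data (Week 16 ppPASI and adverse events to Week 32) continues to be attempted unless the patient withdraws consent. The wording about removal from the trial should be brought into line with that, and the trigger and decision-maker should match the section cited. How trial medication is handled in a non-compliant patient is for the sponsor to settle.

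The cost is one sentence in the protocol. No visits are added, since those needed are already in the flow chart.

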5.0 VARIABLES AND THEIR ASSESSMENT

5.1 TRIAL ENDPOINTS

5.1.1 Primary Endpoint(s)

- Efficacy: ppPASI50 at week 16
- Safety: Number of patients with drug-related AEs

5.1.2 Secondary Endpoint(s)

- Treatment success defined as achieving a clinical response of 0 or 1=clear/almost clear via PPP Physicians Global Assessment (pppPGA) at week 16
- ppPASI75 at week 16
- Percent change from baseline in the ppPASI at week 16

5.2 ASSESSMENT OF EFFICACY

Palmoplantar Pustulosis Physician Global Assessment (pppPGA)

pppPGA relies on clinical assessment of the patient's skin presentation on the palms and soles and will be measured at the timepoints scheduled in the [Flow Chart](#). The investigator

(or qualified site personnel) scores the lesions on the most severely affected palmoplantar surface from 0 – 4 as clear, almost clear, mild, moderate or severe (cf Table 5.2: 1; [R17-0324](#)). Further practical guidance will be available in the ISF.

Table 5.2:1 PPP Physician Global Assessment (pppPGA)

Score	Wording	Detailed description
0	Clear	No signs of PPP; no scaling or crusts or pustule remains
1	Almost clear	Slight scaling and/or erythema and / or slight crusts; very few new (yellow) and / or old (brown) pustules
2	Mild	Scaling and/or erythema and/or crusts; visible new (yellow) and/or old (brown) pustules of limited number and extent
3	Moderate	Prominent scaling and/or erythema and / or crusting; prominent new (yellow) and / or old (brown) pustules covering most of the area involved
4	Severe	Severe scaling and/or erythema and / or crusting; numerous new (yellow) or old (brown) pustules with and/or without major confluence covering the entire area of at least 2 palmoplantar surfaces

Palmoplantar Pustulosis Psoriasis Area and Severity Index (ppPASI)

The ppPASI is an investigator assessment of the extent and severity of pustular and plaque lesions on the palms and soles presenting in PPP patients. The adaptation from PASI, an established measure of severity and area of psoriatic lesions in patients with psoriasis, by Bhushan et.al [[R16-5334](#)] will be used in this trial (cf Table 5.2: 2).

This tool provides a numeric scoring for patients overall PPP disease state, ranging from 0 to 72. It is a linear combination of the percent of surface area of skin that is affected on the palms and soles of the body and the severity of erythema, pustules, and scaling (desquamation).

The ppPASI will be measured at the timepoints scheduled in the [Flow Chart](#).

Table 5.2:2 Palmoplantar Pustulosis Psoriasis Area and Severity Index

Score	0	1	2	3	4	5	6
Erythema (E)	None	Slight	Moderate	Severe	Very severe		
Pustules (P) (total)	None	Slight	Moderate	Severe	Very severe		
Desquamation (D) (scaling)	None	Slight	Moderate	Severe	Very severe		
Area affected (%)*	0	<10	10<30	30<50	50<70	70<90	90 - 100

* where area assessed is glabrous skin on the palms/ soles

Proprietary confidential information © 2018 Boehringer Ingelheim International GmbH or one or more of its affiliated companies

PPPASI = [(E+P+D) Area x 0.2 (right palm)] + [(E+P+D) Area x 0.2 (left palm)] + [(E+P+D) Area x 0.3 (right sole)] + [(E+P+D) Area x 0.3 (left sole)]

5.3 ASSESSMENT OF SAFETY

Safety will be assessed descriptively based on:

- Adverse events (including drug-related AEs)
- Serious adverse events
- Intensity of adverse events will be assessed by Rheumatology Common Toxicity Criteria (RCTC) version 2.0 (refer to ISF for details)
- Safety laboratory tests
- Physical examination
- Vital signs (blood pressure, pulse rate, body temperature)
- 12-lead ECG

5.3.1 Physical examination

Complete and target physical examinations will be performed at visits as described in the [Flow Chart](#). Height and weight of the patient will be recorded at the screening visit.

Complete physical examination will include vital sign assessment and general appearance as well as evaluation of all organ systems. Targeted physical examination will include vital sign assessment and evaluation of organ systems associated with AE(s) symptoms or laboratory abnormalities.

Clinically relevant abnormal findings will be reported as baseline conditions or AEs.

5.3.2 Vital Signs

Vital signs evaluations will be performed at visits as shown in the Flow Chart. This includes measuring temperature, pulse rate, systolic/diastolic blood pressure and respiratory rate. Respiratory rate, pulse rate, and blood pressure will be measured after patients have been sitting comfortably for at least five minutes. All recordings should be made using the same type of blood pressure recording instrument on the same arm if possible.

Measurement of vital signs should precede blood sampling to avoid the impact of blood sampling on the vital measurements. At visits with study drug administration vital signs will be assessed pre-dose, at 5 minutes and approximately 120 minutes after study drug administration.

Patients should be closely monitored for signs and symptoms of hypersensitivity reactions for approximately 2 hours after the study drug administration. Hypersensitivity reactions should be treated according to medical standards. Pre-medications for further injections might be considered and will be agreed on between investigator and BI clinical monitor.

Anaphylaxis is a serious allergic reaction that is rapid in onset and may cause death [R11-4890]. To be able to prospectively define and assess any potential cases of anaphylaxis, the clinical criteria for diagnosis of anaphylaxis defined in [Section 10.1](#) are to be considered.

5.3.3 Safety laboratory parameters

The laboratory tests listed in Table 5.3.3: 1 will be performed at the central laboratory service provider. Samples will be taken and sent for testing at the central lab however in cases of immediate patient safety concerns a local laboratory may be used for selected testing.

Instructions regarding sample collection, sample handling/ processing and sample shipping are provided in the Laboratory Manual in ISF. For time points of laboratory sampling, see [Flow Chart](#).

Laboratory results (i.e. all safety laboratory and clinical laboratory data relevant for current clinical practice) of the patients will be available in real time to the respective investigator (via laboratory reports) and to the sponsor (via the central laboratory website) and selected abnormal laboratory alerts will be flagged to the site and sent to sponsor in real time.

Clinically relevant abnormal findings will be reported as baseline conditions or AE's. A clinically relevant value may be either in- or outside the reference range. Clinically relevant abnormal laboratory test results should be confirmed using an unscheduled visit laboratory kit and should be repeated until normalization or stabilization or until an alternative explanation has been found. Abnormal laboratory values will be also graded for intensity by using RCTC Version 2.0 criteria [R13-3515].

Table 5.3.3: 1 Laboratory tests

Category	Test name
Haematology	Hematocrit (Hct) Hemoglobin (Hb) Glycosylated Hbc (HbA1c) (only at screening) Red Blood Cell Count Reticulocyte Count White Blood Cells / Leukocytes Platelet Count/ Thrombocytes
Diff. Automatic	Neutrophils (relative count) Eosinophils (relative count) Basophils (relative count) Monocytes (relative count) Lymphocytes (relative count)

Table 5.3.3: 1 Laboratory tests (cont`d)

Category	Test name
Diff. Manual (if Diff Automatic is abnormal)	Neutrophils, bands (Stabs) Neutrophils, polymorphonuclear (PMN) Eosinophils Basophils Monocytes Lymphocytes
Coagulation	Partial Thromboplastin Time (aPTT) Prothrombin time (INR) Fibrinogen
Enzymes	AST (GOT) ALT (GPT) Alkaline Phosphatase (AP) Creatine Kinase (CK) CK-MB, only if CK is elevated Gamma-Glutamyl Transferase (GGT/ γ -GT) Lactic Dehydrogenase (LDH) Amylase Lipase Serum tryptase ¹
Electrolytes	Calcium Sodium Potassium Chloride Bicarbonate
Substrates	Glucose BUN (blood urea nitrogen) Uric acid Creatinine eGFR (estimated by CKD-EPI formula) (only at screening) Bilirubin Total Bilirubin Direct (if total is elevated) Bilirubin Indirect (if total is elevated) Troponin (Reflex, in case of elevated CK) Protein, Total Albumin C-Reactive Protein (CRP) (high sensitivity) Cholesterol, total Triglycerides LDL-Cholesterol HDL-Cholesterol
Specific gamma-globulin quantification	IgE ³
Urine Pregnancy test ² . At the drug administration visits, the test will be performed prior to the administration of study drug	Human Chorionic Gonadotropin in urine
Serum Pregnancy test ² (only for female patients of childbearing potential)	Human Serum Chorionic Gonadotropin
Hormones (only at screening)	TSH (free T3 and free T4 in case of abnormal TSH result)
Autoantibodies (only at screening)	Rheumatoid Factor anti-CCP antibodies

Table 5.3.3: 1 Laboratory tests (cont'd)

Category	Test name
Urinalysis (dipstick)	Urine Nitrite Urine Protein Urine Glucose Urine Ketone Urobilinogen Urine Bilirubin Urine RBC/ Erythrocytes Urine WBC/ Leukocytes Urine pH Urine creatinine
Urine-Sediment (microscopic examination, only if urine analysis abnormal)	Urine Sediment Bacteria Urine Cast in Sediment Urine Squamous Epithelial Cells Urine Sed. Crys., Unspecified Urine Sediment RBC/ Erythrocytes Urine Sediment WBC/ Leucocytes
Urine (only at screening)	Albumin (quantitative)
Infections screening (only at screening)	Hepatitis B Surface Antigen (qualitative), Hepatitis C Antibodies (qualitative), HIV-1, and HIV-2 Antibody (qualitative), QuantiFERON®

¹performed only at the randomisation visit (visit 2).

²Urine and serum pregnancy testing will be performed as indicated in the [Flow Chart](#).

³IgE will be taken in case of infusion reaction together with ADA (anti-drug antibodies) sample

5.3.4 Electrocardiogram

The 12-lead ECGs will be performed as scheduled in the Flow Chart.

ECGs will be recorded after the patients have rested for at least 5 minutes in a supine position and will always precede blood sampling to avoid impact of sampling on results. Six limb leads, as specified by Einthoven (I, II and III) and Goldberger (aVR, aVL, aVF), and six pre-cordial leads (V1–V6), according to Wilson, will be used.

ECGs may be repeated for quality reasons (like alternating current artefacts, muscle movements, electrode dislocation).

Additional ECGs may be collected for safety reasons. Clinically relevant, abnormal findings will be reported as AEs.

The electronic version, if applicable, or dated and signed printouts of the ECG will be regarded as source data and stored in the patient's medical file.

5.3.5 Other safety parameters

5.3.5.1 Medical examination

At the screening visit, the medical examination will include documentation of patient information, informed consent, demographics including height and body weight, smoking and alcohol history, relevant medical history and concomitant therapy, review of inclusion and exclusion criteria, review of vital signs (BP, PR), 12-lead ECG, laboratory tests, and a physical examination. Details about the timing of the examinations during the trial are included in the [Flow Chart](#).

